8.4 Safety Assessments

Safety will be assessed for all enrolled patients from the time of signing the informed consent up to 7 days after the final study visit (month 9). Safety parameters include pulmonary function testing (PFT, including FVC, FEV1, MIP, MEP), physical examination, vital signs and –at decision of investigator- clinical laboratory tests as needed. See also Section 9.

9 ADVERSE EVENTS REPORTING (AE)

A deterioration of >15% of FVC in comparison to baseline measurements will be defined as an AE, as well as developing unusual myalgia of respiratory muscles for more than 12 hours. AEs and SAEs will be coded using the Medical Dictionary for Regulatory Activities and summarized by primary system organ class and preferred term. Detailed listings of patients who experience AEs or SAEs will be presented. The incidence of treatment-emergent AEs and SAEs will be tabulated (frequencies and percentages) by severity, and by relationship to treatment. Adverse event severity will be categorized as mild, moderate, or severe. In tabulating severity of AEs on a per patient basis, the greatest severity will be assigned to a patient should there be more than one occurrence of the same AE with different reported severities. Relationships of the AE to treatment will be categorized as not related, unlikely related, possibly related, or related. The highest level of association will be reported in patients with differing relationships

for the same AE. Listings of AEs and SAEs for all patients will be provided, which will include severity and relationship to treatment, as well as actions taken regarding treatment, and patient outcome. A separate listing for patients who withdraw from the study due to AEs will be provided. The incidence of AEs leading to study discontinuations will also be summarized.

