All patients who participate in this study will be included in the analysis. Data collected in this study will be documented using summary tables, figures, and patient data listings. For continuous variables, descriptive statistics (n, mean, median, standard deviation, minimum, and maximum) will be presented. For categorical variables, frequencies and percentages will be presented. Graphical displays will be presented as appropriate.

Power and Sample Size:

This is an exploratory study about efficacy and safety of respiratory muscle training in patients with Myotonic Dystrophy Type 1 and is not powered to make other statistical inferences.

Analysis-Sets:

Full Analysis Set: This analysis set consists of all patients who performed respiratory muscle therapy for at least 9 months or who did the check-ups throughout the 9 months without respiratory muscle training. All analyses will be based on this analysis set

Demographics and Baseline Characteristics:

Demographic and baseline data on medical/surgical history and disease history including length of repeats will be summarized using descriptive statistics for continuous variables and frequency distribution for categorical variables.

Safety:

A deterioration of >15% of FVC in comparison with baseline measurements will be defined as an AE, as well as developing unusual myalgia of respiratory muscles for more than 12 hours. The Adverse events will be collected from enrollment (=signed informed consent) through month 9 plus 7 days. Adverse events will be coded using the Medical Dictionary for Regulatory Activities, and categorized by system organ class and preferred term. All AEs will be displayed in patient listings. Adverse events will be categorized and tabulated for the treatment group overall by severity, seriousness, and relationship to study treatment

Efficacy:

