Observed measurements and changes from baseline to each study time point in respiratory function parameters (% predicated sitting and supine FVC, forced expiratory volume in the 1st second of the FVC maneuver [FEV1], maximal inspiratory pressure [MIP], maximal expiratory pressure [MEP], and peak expiratory flow [PEF]); and blood gas analysis (pH, pCO₂, pO₂) as well as oxygen saturation and six-minute-walk-test with Borg scale will be summarized using descriptive statistics. In addition, 95% confidence intervals will be used to estimate the change from baseline at each study visit. Graphical displays showing data over time will be presented as appropriate.

REFERENCE TREATMENT:

There is no reference treatment to respiratory muscle training.

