7.2 End Points

7.2.1 Safety end points

Routine safety assessments are considered as primary endpoints of this study and are described in the sections 8, 9, 10 and 11.

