8.3.3 Pulmonary Function Testing

PFT will be performed at time points specified in Appendix A. The PFT administration protocol will be standardized in accordance with the American Thoracic Society (ATS) guidelines (American Thoracic Society/European Respiratory 2002). PFT will include the assessment of

forced vital capacity (FVC), forced expiratory volume in the 1st second of the FVC maneuver (FEV1), maximal inspiratory pressure (MIP), maximal expiratory pressure (MEP), and peak expiratory flow (PEF) in the upright and supine positions.

FVC is the maximal volume of gas that can be exhaled with the patient breathing forcefully to obtain maximal airflow rates. For this measurement, the patient is instructed to inspire completely until the lungs are fully inflated. A nose clip is used to prevent leakage. Then the patient exhales as far as possible until the lungs are almost empty and the measured volume is recorded. Data are reported in liters and percent of predicted normal values based on age, gender, race, and height (Hankinson, Odencrantz et al. 1999).

Respiratory status will be assessed by spirometry using the KoKo PFT System © 2010 nSpire Health Inc. spirometer. FVC and FEV1 will both be measured in upright and supine position. In addition, the function of the respiratory muscles will be evaluated by the maximal respiratory pressures MIP for maximum inspiratory pressure and MEP for maximum expiratory pressure. For MIP and MEP in upright position, the CareFusion digital manometer from microRPM™ will be used with a flanged mouthpiece, as recommended by the American Thoracic Society (ATS) (American Thoracic Society/European Respiratory 2002). Calibration of software and spirometry devices will be done daily, as described in software manuals (Bolliger, Mathur et al. 2002).

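### The FVC adverse-event rule fixes neither position nor scale, and under Appendix A the training arms have more chances to trigger it than the control arm

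*Protocol*

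**What the plan says.** The rule stands twice in the protocol with the same content. The Synopsis (Safety) has "A deterioration of >15% of FVC in comparison with baseline measurements will be defined as an AE" and Section 9 has "A deterioration of >15% of FVC in comparison to baseline measurements will be defined as an AE". The Section 9 sentence continues with a second quantified rule: "as well as developing unusual myalgia of respiratory muscles for more than 12 hours". Neither place names a position, or says whether 15% is relative or in percentage points.

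Section 8.3.3 produces several candidate FVC values at each test: "FVC and FEV1 will both be measured in upright and supine position" and "Data are reported in liters and percent of predicted normal values based on age, gender, race, and height".

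On the weight of the rule, Section 7.2.1 states: "Routine safety assessments are considered as primary endpoints of this study". Section 8.4 lists FVC among the safety parameters, together with the other lung-function measures, physical examination and vital signs.

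On the schedule, Appendix A marks lung-function testing, sitting and supine, at months 1, 3, 5, 7 and 9 for groups 1 and 2. For group 3 it marks months 5 and 9 only. Its adverse-event row is marked at all five follow-up visits in every group. The Synopsis (Study Procedures) instead gives all patients six lung-function tests, counting screening.

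**The concern.** An adverse event defined by a threshold on a repeated measurement becomes more likely each time the measurement is taken. Under Appendix A a trained patient can cross the threshold at five visits and a control patient at two. At months 1, 3 and 7 a control patient is asked about adverse events but cannot have this one detected, because FVC is not measured. Set side by side, the arms would then show more FVC events under training even if training did nothing.

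The open definition adds to this. Staff who count a fall in either position will record more events than staff who count sitting FVC only, and both follow the text. With 15 patients per arm, a difference of one or two patients would shape how the safety result is read.

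**Working it through.** **Plan's own figure.** There is none to reproduce. The protocol gives no expected event rate, no FVC variability and no sample-size calculation (Section 10.2).

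**Inputs from the protocol.** Threshold: a fall of more than 15% from baseline. Positions: 2. Follow-up FVC visits in Appendix A: 5 in groups 1 and 2, 2 in group 3. Readings per patient: 5 × 2 = 10 against 2 × 2 = 4. Patients per arm: 15.

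**Assumptions, not in the protocol.** No true change in any arm. Normal noise, independent between visits, with single-reading SD (sitting/supine) of 3/3.5%, 4/5%, 6/7% or 8/9%. Correlation of 0.6 between the two positions at one visit. One noisy baseline reading per position, shared by all follow-up visits. The 15% is read as relative.

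**One reading.** Let e0 and e1 be the noise at baseline and follow-up. The rule is met when (1 + e1)/(1 + e0) < 0.85, that is, e1 − 0.85·e0 < −0.15. The left side has SD σ·√(1 + 0.85²) = 1.312σ. For sitting FVC at one visit:

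- σ = 4%: z = −0.15/0.0525 = −2.86, probability 0.2%
- σ = 6%: z = −0.15/0.0787 = −1.91, probability 2.8%
- σ = 8%: z = −0.15/0.1050 = −1.43, probability 7.7%

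**All readings.** Visits share a baseline and positions are correlated, so the chance of at least one flagged reading was simulated (400,000 patients per row; repeat runs agree to about 0.2 points).

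| Noise SD, sitting/supine | Trained, either position, 5 visits | Control, either position, 2 visits | Trained ÷ control | Trained, sitting only, 5 visits | Either ÷ sitting |
|---|---|---|---|---|---|
| 4/5% | 5.3% | 2.4% | 2.2 | 1.0% | about 5 |
| 6/7% | 23.6% | 12.3% | 1.9 | 10.9% | 2.2 |
| 8/9% | 42.1% | 24.5% | 1.7 | 25.3% | 1.7 |

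At 3/3.5% the trained and control rates are 0.3% and 0.1%, or 15 × 0.003 ≈ 0.04 trained patients per arm.

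**In an arm of 15** (15 × rate, either position), trained against control:

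- 4/5%: 0.8 against 0.4
- 6/7%: 3.5 against 1.8
- 8/9%: 6.3 against 3.7

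**With the fix** (sitting only, months 5 and 9 in every arm), the noise-only rate is 0.4%, 5.3% and 13.5% at sitting SD 4%, 6% and 8%. It is the same in all arms, so the schedule-driven ratio is 1.

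**The case against.** The strongest reply has four parts.

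**Analysis detail.** Position and scale are derivation choices that an SAP may settle, and Section 10.6 lists the data by patient and visit, so a threshold can be recomputed. This stands for stored FVC values. It does not restore readings that group 3 never had. Nor does it make consistent the events that were recorded, graded and coded at the visits under different understandings of the rule.

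**A descriptive pilot.** Section 10.1 plans no formal tests, and FVC change is also summarised at each visit with 95% confidence intervals. That limits the damage. But the descriptive tables are then the result, and a control arm invites the comparison.

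**The schedule is contradictory.** If the Synopsis governs, with six tests for everyone, the gap between arms disappears. This is correct, so the ratio is conditional on Appendix A.

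**Plain meaning.** A 15% fall from baseline is most naturally relative, and on that reading litres and percent predicted give practically the same answer over nine months. This also stands. The real scale question is relative change against percentage points.

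A reader might also infer stronger claims that the protocol does not support:

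- *This is the only quantified safety rule.* The same sentence contains the 12-hour myalgia rule.
- *The events would mostly be test noise.* That depends on a variability the protocol does not give, and at about 3% noise they are negligible.
- *The count could vary some 20-fold.* That needs the less natural percentage-point reading. From a baseline of 70% predicted, 15 points is 15/70 = 21.4% relative, which few noise-only readings reach.
- *The primary safety result hangs on this rule.* Section 7.2.1 makes routine safety assessments as a whole primary.

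**Conclusion.** The point holds as a defect of definition and schedule in one component of the primary safety endpoint. Position and scale are open on the face of the text. If Appendix A is followed, noise alone flags about 1.7 to 2.2 times as many trained as control patients, a bias against training. Counting either position rather than sitting only multiplies the trained-arm count about 1.7 to 5 times.

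These ratios rest on an assumed noise SD of 4% to 9%, a between-position correlation of 0.6 and no true change. The absolute number of spurious events is far more sensitive to the noise level than the arm ratio is: from under one trained patient in 15 at 4/5% to about six at 8/9%. The existence and direction of the schedule effect follow from five visits against two and do not depend on the exact SD. It should be corrected, and correction is cheap.

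**What to change.** 1. Keep the sponsor's 15% figure. In the Synopsis and Section 9, state that for the endpoint count it means relative change from Visit 1 in one named position, for example sitting FVC in litres. Tabulate supine falls separately.
2. For the between-arm comparison, count only falls at months 5 and 9, where Appendix A measures FVC in all three groups. List falls at other visits descriptively by arm.
3. Reconcile the Synopsis (six lung-function tests for every patient) with Appendix A (three in group 3).

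The cost is a sentence or two in each place. The downside is that falls seen only at months 1, 3 or 7 leave the comparison, though they stay in the adverse-event listings. The fix equalises the noise between arms but does not remove it. A confirmatory repeat manoeuvre would be an added procedure and is not needed for this purpose. Adverse-event reporting and the clinical response to a falling FVC are unchanged.

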10 STATISTICAL METHODS AND PLANNED ANALYSES

10.1 General Considerations

Data collected in this study will be reported using summary tables, figures and patient data listings. Summary statistics (n, mean, median, standard deviation, minimum and maximum) will be calculated for the continuous variables and shift tables and/or frequencies, and percentages will be produced for the categorical variables. Due to the exploratory nature of this study, no formal inferential statistical tests will be performed.

10.2 Determination of Sample Size

Approximately 45 patients will be enrolled in this study. No formal sample size calculations have been performed. This is an exploratory study and is not powered to make any statistical inferences.

10.3 Demographics and Baseline Characteristics

Demographic and baseline data on medical/surgical history and DM1 disease history including molecular genetics will be summarized using summary statistics for continuous variables and frequency distribution for categorical variables. All data will be presented in by-patient listings.

10.4 Patient Accountability

Data from all patients who are enrolled in the study will be included in the summary of patient accountability. The frequency and percentage of patients who are enrolled in the study, discontinued from the study, and completed the study, along with reasons for discontinuation, will be summarized.

10.5 Study Training and Compliance

The number of days/weeks/months on which the training is carried out and the number of study training sessions carried out by patients are summarised using summary statistics.

10.6 Efficacy Analyses

Observed measurements and changes of the respiratory function parameters (FVC, FEV1 sitting and lying, MIP, MEP) up to the time of the study and health-related questionnaires on quality of life and symptoms of respiratory insufficiency are summarised using summary statistics. In addition, 95% confidence intervals will be used to estimate the change from baseline at each study visit. All data will be presented by study visit in by-patient listings.

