1 SYNOPSIS

TITLE: DMIMT - Controlled, randomized, three-arm interventional study on safety and efficacy of regular respiratory muscle training in patients with myotonic dystrophy type 1
PROTOCOL-NUMBER: Version 1.2 (26. June 2019)
STUDY CENTRE/CLINIC/INSTITUE: Friedrich-Baur-Institute, Klinikum der Universität München, [name], Germany
OUTCOME MEASURE: The primary objective of this study is to investigate the safety of repetitive respiratory muscle training on respiratory muscle strength measured by MIP (maximum inspiratory pressure) in the upright position. The secondary objectives are 
• Efficacy and safety of repetitive inspiratory strength muscle training in 15 patients with myotonic dystrophy type 1,• Efficacy and safety of repetitive inspiratory endurance muscle training in 15 patients with myotonic dystrophy type 1,• Measurement of the effect on the quality of life and muscular performance in patients with myotonic dystrophy type 1 during respiratory muscle training or in patients without respiratory muscle training, measured using the questionnaires "DM1-Activ", "Respicheck" and "FDSS-Fatigue and Daytime Sleepiness-Scale".• Measurement of the influence on CO₂ and O₂ values in capillary blood gas analysis of patients with myotonic dystrophy type 1 during respiratory muscle training or in patients without respiratory muscle training.• Measurement of the impact of respiratory muscle training on the 6-minute walking test in patients with DM1.

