6 STUDY OBJECTIVES

The primary objective of this study is to determine the safety of repetitive respiratory muscle training on respiratory muscle strength as measured by MIP (maximum inspiratory pressure) in the upright position.

The secondary objectives are to evaluate the

- efficacy and safety of repetitive inspiratory strength respiratory muscle training in 15 patients with myotonic dystrophy type 1,
- efficacy and safety of repetitive inspiratory endurance respiratory muscle training in 15 patients with myotonic dystrophy type 1,
- Measurement of the effect on the quality of life and muscular performance in patients with myotonic dystrophy type 1 during respiratory muscle training or in patients without respiratory muscle training, using the questionnaires "DM1-Activ", "Respicheck" and "FDSS-Fatigue and Daytime Sleepiness-Scale",
- Measurement of the effect on the values CO₂ and O₂ in capillary blood gas analysis of patients with myotonic dystrophy type 1 during respiratory muscle training or in patients without respiratory muscle training,
- Measurement of the effect on muscular endurance performance in patients with myotonic dystrophy type 1 during respiratory muscle training or in patients without respiratory muscle training, measured by the 6-minute walking test.

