7.1 Discussion of study design, including choice of control group

This is a monocentric, three-arm, controlled interventional study for patients with myotonic dystrophy type 1. The patient is not blinded regarding his group assignment (group 1 and 2:

respiratory muscle therapy, group 3 control group without respiratory muscle therapy). The efficacy and safety of regular training of the respiratory muscle on the patient's health status is to be investigated.

The endpoints for this study are changes from baseline to month 9 after repetitive training.

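### The only interval planned in this randomised three-arm trial is on change from baseline; no stated estimate uses the untrained control, and adverse events are not tabulated by arm

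*Protocol*

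**What the plan says.** The title calls the trial a "Controlled, randomized, three-arm interventional study on safety and efficacy of regular respiratory muscle training". Appendix B gives three groups of 15, one of them untrained.

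**Efficacy.** Section 7.1 states: "The endpoints for this study are changes from baseline to month 9 after repetitive training". Section 10.6 and the Efficacy part of the synopsis both plan summary statistics and add that "95% confidence intervals will be used to estimate the change from baseline at each study visit". Neither states a difference between arms. Section 10.1 says: "Due to the exploratory nature of this study, no formal inferential statistical tests will be performed". Three secondary objectives in section 6 concern an effect "during respiratory muscle training or in patients without respiratory muscle training".

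**Safety.** Section 7.2.1 makes routine safety assessments primary, and section 6 asks for the safety of strength training and of endurance training as two separate objectives. The Safety part of the synopsis says: "Adverse events will be categorized and tabulated for the treatment group overall by severity, seriousness, and relationship to study treatment". Section 9 tabulates by severity and relationship and names no arm.

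**Population.** The synopsis says: "All patients who participate in this study will be included in the analysis". Its Analysis-Sets paragraph then defines a full analysis set of patients who trained, or attended check-ups, for nine months, and rests every analysis on it. Section 8.4 assesses safety in all enrolled patients.

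**The concern.** A change from baseline in a training arm is the sum of the training effect and whatever would have happened without training. The second part may be practice with the MIP manoeuvre, regression to the mean, or the slow progression described in the Introduction. It can flatter training or hide a benefit. Randomising an untrained arm is the means of removing it, but no stated estimate does so.

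On safety, one column for the treatment group overall could mean both training arms or all patients. Under either reading it cannot show whether one training mode carries the events, although the objectives ask about each mode.

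A population chosen by completing nine months is no longer the randomised one. It can also leave out of the analysis patients who stopped because of an adverse event.

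**Working it through.** The protocol states no power, effect size, SD or expected change, so there is no figure of its own to reproduce. What follows is an illustration in units of the SD of change.

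**Inputs.** n = 15 per arm (Appendix B). Assumed: by-arm intervals, normal changes with equal SD, and a shared change c in every arm of 0.1, 0.25 or 0.5 SD.

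**Step 1: coverage of the training effect by a within-arm interval.** With t(0.975; 14) = 2.145 and T noncentral t with 14 df and noncentrality c√15,

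coverage = 1 − P(T > 2.145) − P(T < −2.145).

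| c | c√15 | upper tail | lower tail | within-arm coverage | between-arm coverage |
|---|---|---|---|---|---|
| 0.1 | 0.387 | 0.055 | 0.010 | 0.935 | 0.95 |
| 0.25 | 0.968 | 0.145 | 0.002 | 0.853 | 0.95 |
| 0.5 | 1.936 | 0.438 | 0.000 | 0.562 | 0.95 |

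The result does not depend on the size of the training effect, and coverage is the same for a shared loss. In the between-arm difference c cancels.

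**Step 2: apparent benefit when there is none.** This step matters only to a reader who takes an interval above zero as benefit; the protocol states no such rule. Let p be the upper tail above. The chance that at least one training arm's interval lies above zero while the control's does not is [1 − (1 − p)²](1 − p):

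- c = 0.25: 0.27 × 0.855 = 0.23
- c = 0.5: 0.684 × 0.562 = 0.38

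For comparison, at least one of the two between-arm intervals lies above zero in about 4.5% of trials (simulation, shared control).

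**Step 3: width.**

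- Within arm: 2.145/√15 = 0.55.
- Between arms, unadjusted: t(0.975; 28) × √(2/15) = 2.048 × 0.365 = 0.75. With 12 per arm it is 0.85.
- Adjusted for baseline MIP only (41 df), assumed baseline to month-9 correlation 0.5 to 0.9: about 0.645 to 0.72 (simulation).
- With three to six further terms that predict nothing: about 0.67 to 0.79.

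**Step 4: pooled adverse events (assumed counts).** A pooled 6/30 (20%) fits 3/15 in each training arm. It fits equally 6/15 (40%, exact 95% interval 16 to 68%) in one and 0/15 (0 to 22%) in the other.

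**Step 5: visits at which arms can be compared.** Appendix A gives the training arms lung function and MIP at months 0, 1, 3, 5, 7 and 9, and the control arm at months 0, 5 and 9. An FVC fall of more than 15% counts as an adverse event, so the training arms have five chances to record one and the control arm two. The Study Procedures part of the synopsis instead gives all patients six lung function tests. Months 5 and 9 are common to all arms under either schedule.

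**The case against.** The strongest objection is that a statistical analysis plan, not shown, may add contrasts and by-arm tables, and that a protocol commonly leaves these to it. A change from baseline is also a patient-level variable that a between-arm contrast would itself use, so section 7.1 alone proves nothing. The study is a pilot, not powered for inference (section 10.2), and efficacy is not primary (section 7.2.2). Part of this stands: the trial is not invalidated, and the absence of tests is no fault. But the protocol is not merely silent. It fixes the interval twice, names an adverse-event grouping that merges the training modes, and fixes a completer population. A difference with an interval is an estimate, which section 10.1 does not exclude.

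Several stronger readings are tempting, and the documents do not support them:

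- A reader might infer that the control would play no part. If intervals are given by arm, the control has its own, and side by side they would show shared drift. The chance of any training interval above zero, 27 and 68% at c = 0.25 and 0.5, ignores this; requiring that the control's interval is not above zero gives 23 and 38%. Setting intervals side by side still does not estimate a difference.
- A reader might infer that safety is confined to completers or that events are lost. Section 8.4 covers all enrolled patients, and section 9 lists events for all patients and summarises those leading to discontinuation. What stands is the conflict with the synopsis and the lack of a stated count by arm.
- A reader might infer from section 7.6 that patients who stop training would be analysed as controls. It calls them suitable for admission to the control group; no section says how they are analysed.
- A reader might compute the excess of FVC-defined events from five independent checks. Each check uses the same baseline, so the errors correlate and that calculation overstates the excess.

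**Conclusion.** The point holds and should be acted on before analysis. As written, the plan's only interval estimates training effect plus shared change, its synopsis table merges the safety of two modes that the objectives separate, and its completer rule contradicts both its own opening sentence and section 8.4.

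The sizes rest on assumed drift. If drift is nil, the within-arm interval has its nominal coverage and is narrower; at half an SD it misses the training effect in 44% of trials.

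The between-arm estimate is not a full remedy. Patients are not blinded, and under Appendix A the training arms perform MIP at six sessions and the control arm at three. If these alone favour training by an assumed 0.1, 0.25 or 0.5 SD, between-arm coverage is 94, 90 or 74%.

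The unclear role of MIP is a separate matter. It is the measure in the primary objective, worded as the "safety of repetitive respiratory muscle training on respiratory muscle strength as measured by MIP", and a safety parameter in section 8.4, yet an efficacy measure in section 8.3, and section 7.2.2 says efficacy is not primary. The two lung function schedules are likewise a separate conflict. Neither is needed for the main conclusion.

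**What to change.** 1. In section 10.6, add the difference between each training arm and control in month-9 upright MIP, with a 95% confidence interval and no hypothesis test. Adjust for baseline MIP and for those of MIRS, age and gender actually used to stratify randomisation, fixed in advance and coded sparingly. Sections 10.1 and 10.2 can stand.
2. Use all randomised patients with month-9 data, in the arm to which they were randomised, whether or not they stopped training. Report by arm how many lack month-9 MIP. Reconcile the wording of section 7.6 with this.
3. Tabulate adverse events by the three randomised arms for all enrolled patients. Compare FVC-defined events between arms only at months 5 and 9.
4. Separately, reconcile the two population statements in the synopsis, the lung function schedule in the synopsis with Appendix A, and the role of MIP across the synopsis and sections 6, 7.2.1, 7.2.2, 8.3 and 8.4.
5. State with the result that lack of blinding and unequal MIP practice may bias the contrast.

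The work is one regression model, one table layout and text edits, without new measurements. The statistical price is the wider interval shown in step 3. Many covariate terms can cancel the gain from adjustment: with six non-predictive terms and a correlation of 0.9, the half-width is about 0.79, above the unadjusted 0.75. That is the reason for sparing coding.
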